## List of Abbreviations

Abbreviation	Definition
%	Percentile
ACDS	Adult Clinician Diagnostic Scale
ADD	Attention Deficit Disorder
ADHD	Attention Deficit Hyperactivity Disorder
ADHD-C	Attention Deficit Hyperactivity Disorder Combined type
ADHD-HI	Attention Deficit Hyperactivity Disorder-Hyperactive Impulsive type
ADHD-I	Attention Deficit Hyperactivity Disorder-Inattentive type
AE	Adverse Events
ADHD-RS	ADHD Rating Scale
AMP	Amphetamine
AST	Attention Switching Task
BARRS	Barkley SCT Scale
BFIS	Barkley Functional Impairment Scale
BP	Blood Pressure
bpm	Beats per minute
BRIEF-A	Behavior Rating Inventory of Executive Function®-Adult Version
CANTAB	Cambridge Neuropsychological Testing Automated Battery
CRF	Case Report Form
CGI-IS	Clinical Global Impressions-Impairment scale
CI	Confidence Interval

Abbreviation	Definition
C-SSRS	Columbia-Suicide Severity Rating Scale
CM	Concomitant Medications
CT	Clinical Trial
CPOE	Computerized Physician Order Entry system
d/c'd	Discontinued
DEA	Drug Enforcement Administration
DR	Dose Related
DSM	Diagnostic and Statistical Manual of Mental Disorders
DSM-IV	Diagnostic and Statistical Manual of Mental Disorders 4 th edition
ECG	Electrocardiograph
EPIC	Electronic Medical Health Records
f/u	Follow up
FDA	Food & Drug Administration
freq	Frequency
GEE	Generalized Estimating Equation
GLM	General Linear Model
HIPAA	Health Insurance Portability and Accountability Act of 1996
IR	Immediate Release
IDS	Investigational Drug Service
kg	Kilogram
LDX	Lisdexamfetamine Dimesylate
LT	Long-term
MAO	Monoamine Oxidase

Abbreviation	Definition
MAOI	Monoamine Oxidase Inhibitors
MAS	Mixed Amphetamine Salts
MAS XR	Mixed Amphetamine Salts Extended Release
MI	Myocardial Infarction
MINI	Mini International Neuropsychiatric Interview
mg	Milligram
mmHg	Millimeters of Mercury
MPH	Methylphenidate
ON-TOP	On Time Management, Organization, and Planning ON-TOP
QTc	Q T Interval
RCT	Randomized Controlled Trial
SCT	Sluggish Cognitive Tempo
stim	Stimulant
WAIS-IV	Wechsler Adult Intelligence Scale-IV

### Study Summary

Title	EFFICACY OF LISDEXAMFETAMINE IN ADULTS WITH ADHD AND SLUGGISH COGNITIVE TEMPO
Short Title	Shire SCT
Protocol Number	S13-01288
Phase	Clinical study phase 2
Methodology	A phase II, randomized, double-blind, cross-over, multi-center study of the effects of Vyvanse (LDX) vs. placebo with an intervening single-blind placebo washout period on patients with Adult Deficit Hyperactivity Disorder (ADHD) and Sluggish Cognitive Tempo (SCT).
Study Duration	13 weeks
Study Center(s)	Multi-center; NYU and Mount Sinai
Objectives	To examine the effects of Vyvanse (LDX) vs. placebo with an intervening single-blind placebo washout period on patients with Adult Deficit Hyperactivity Disorder (ADHD) and Sluggish Cognitive Tempo (SCT).
Number of Subjects	120 adults (20% screen fail rate), will be recruited to evaluate at the screening visit approximately 100 adults with ADHD at two sites (NYU and Mount Sinai) to identify 50 SCT+ and 50 SCT-.
Diagnosis and Main Inclusion Criteria	The study population will consist of male and female outpatients between 18 and 60 years of age, inclusive, with a Primary diagnosis of ADHD according to Diagnostic and Statistical Manual of Mental Disorders, Fourth Edition, Text Revision (DSM-IV-TR) 16 criteria as determined by the Adult Clinician Diagnostic Scale version 1.2 (ACDS v1.2).

Study Product, Dose, Route, Regimen	Lisdexamfetamine Dimesylate (LDX), Vyvanse. Placebo controlled cross-over study of oral, LDX 30-70 mg/day in SCT+ adults. Participants taking prohibited concomitant medications, including ADHD medications, will be required to washout of their medication during the screening phase. The washout period will be one week for psychostimulants and three weeks for non-stimulants.
Duration of administration	Patients will be assigned either LDX/Placebo for 10 weeks with a two week placebo washout period.
Reference therapy	Reference is a placebo.
Statistical Methodology	During the phenotype phase: Comparisons between the adult ADHD patients cohorts with SCT and without SCT in terms of ADHD symptoms will be examine via One Way ANOVA . Treatment Phase: Changes in outcome ratings in the patients in the treatment phase with LDX and placebo will be modeled with longitudinal generalized estimating equation (GEE) mixed regression models using STATA 12.0 [StataCorp, 2011 #25856] within the framework of the general linear model (GLM).

## **1 Introduction**

This document is a protocol for a human research study. This study is to be conducted in accordance with US government research regulations, and applicable international standards of Good Clinical Practice, and institutional research policies and procedures.

### **1.1 Background**

SCT describes individuals who are “dreamy”, “spacey”, slow moving, hypoactive, have difficulty initiating tasks, and often seem under-motivated and under-aroused. In a population sample of 1,249 adults with and without ADHD, and with and without SCT, Barkley identified nine cardinal symptoms of SCT: 1) prone to daydreaming instead of concentrating; 2) trouble staying alert/awake in boring situations; 3) being easily confused; 4) being easily bored; 5) feeling spacey/in a fog; 6) frequently feeling lethargic; 7) being underactive/having less energy than others; 8) being slow moving; 9) not processing information quickly/accurately [1]. Individuals were identified as SCT if they had at least 5 of 9 symptoms rated often or very often on the 9-item SCT subscale from the Barkley Adult ADHD Rating Scale-IV: Self-Report (BAARS-IV; hereafter called the Barkley SCT Scale) [2]. The prevalence rate of SCT in this sample was 5.8%, approximately half of whom had ADHD. These results indicate that SCT is common in a large subgroup of adults with ADHD, but is not restricted to ADHD.

SCT may represent a clinically meaningful condition with distinct underlying pathophysiology and treatment response. Several investigators have posited the existence of neurobiologically distinct subtypes of ADHD that are differentially characterized by deficits in executive/inhibitory control, reward-related motivational processes, and state regulation [3-8]. This proposal to investigate treatment response of adults with ADHD and SCT is proposed in that context. To date, there has only been one naturalistic treatment trial of methylphenidate (MPH) in children with ADHD and SCT, which found that the response for SCT was lower than core ADHD symptoms [9].

However, that study was done with MPH. A controlled, clinical trial of LDX in adult ADHD with and without SCT is of critical importance for several reasons:

- 1) SCT is highly co-morbid and impairing in adult ADHD but there have been no controlled treatment studies of SCT in adults.
- 2) The magnitude of response in adults with ADHD and SCT is not known, but it is presumed (possibly incorrectly) from preliminary pediatric data that it may be less robust [9].
- 3) There have been no treatment trials of amphetamines (AMP) in SCT and ADHD.

Examining the efficacy of AMP in SCT is important as the AMP stimulant class is more potent than the MPH class through a dual effect on adrenergic/dopaminergic pathways, which may be important for effects on SCT.

## **1.2 Investigational Agent**

Vyvanse (Lisdexamfetamine Dimesylate) manufactured by Shire, is a DEA class two, sympathomimetic amine. Its indications are for treatment of attention-deficit hyperactivity disorder. The initial adult dosage is 30mg with allowed adjustments in increments of 10mg or 20mg at weekly intervals. The maximum dosage is 70mg/day. Pediatric dosage will not be discussed as we will only recruit adults for this study. Vyvanse is supplied in 20mg, 30mg, 40mg, 50mg, 60mg, and 70mg capsules.

### **Drug interactions with Vyvanse (Lisdexamfetamine Dimesylate)**

Urinary acidifying agents (e.g., ascorbic acid) increase urinary excretion and decrease the T1/2 of the amphetamine, while urinary alkalinizing agents (e.g., sodium bicarbonate) decrease urinary excretion and extend the T1/2 of the amphetamine; adjust dose accordingly. There can be possible contraindications with Vyvanse if used with an MAOI or used within 14 days of the last MAOI dosage.

### **Pregnancy with Vyvanse (Lisdexamfetamine Dimesylate)**

Vyvanse is a Category C and is not for use while pregnant or nursing. There are no adequate and well-controlled studies with Vyvanse in pregnant women. Vyvanse is an amphetamine and its sympathomimetic effects on placental perfusion and fetal blood flow are unknown. Adverse pregnancy outcomes, including premature delivery and low birth weight have been seen in infants born to mothers dependent on amphetamines. Animal reproduction studies performed with lisdexamfetamine dimesylate showed no effects on embryofetal morphological development and survival. Long-term neurochemical and behavioral effects have been seen in animal developmental studies using clinically relevant doses of amphetamine (d- or d,l-). Vyvanse should be used during pregnancy only if the potential benefit justifies the potential risk to the fetus [28].

### **Vyvanse (Lisdexamfetamine Dimesylate) mechanism of action**

Sympathomimetic amine; CNS stimulant. Product of dextroamphetamine. Blocks the reuptake of norepinephrine and dopamine into the presynaptic neuron and increases the releases of these monoamines into the extraneuronal space.

### **Vyvanse (Lisdexamfetamine Dimesylate) Pharmacokinetics**

Absorption: Rapid; Tmax=1 hr (Lisdexamfetamine), 3.5 hrs (Dextroamphetamine).  
Distribution: Found in breast milk. Metabolism: Hydrolysis by RBC;  
Dextroamphetamine (active metabolite). Elimination: Urine (96%; 42%  
amphetamine, 2% unchanged), feces (0.3%); T1/2=<1 hr. (www.nlm.nih.gov).

### **1.3 Preclinical Data**

Vyvanse is approved by the Food and Drug Administration (FDA) for the treatment of ADHD in adults and children. SCT describes individuals who are “dreamy,” “spacey,” slow moving, hypoactive, have difficulty initiating tasks, and often seem under-motivated and under-aroused. This study will determine similarities and differences between adults with ADHD with SCT and adults with ADHD without SCT. This important study will investigate the treatment response of Adults with ADHD

CONFIDENTIAL

and SCT using Vyvanse verses Placebo (sugar pill). Information regarding the clinical presentation of adults with ADHD (those with and without SCT) will establish the potential utility of LDX in the population of adults with ADHD and SCT. As such, this study will address important gaps in the existing treatment literature.

#### **1.4 Clinical Data to Date**

To date, there has only been one naturalistic treatment trial of methylphenidate (MPH) in children with ADHD and SCT, which found that the response for SCT was lower than core ADHD symptoms [9]. However, that study was done with MPH.

A controlled, clinical trial of LDX in adult ADHD with and without SCT is of critical importance for several reasons:

- 1) SCT is highly co-morbid and impairing in adult ADHD but there have been no controlled treatment studies of SCT in adults.
- 2) The magnitude of response in adults with ADHD and SCT is not known, but it is presumed (possibly incorrectly) from preliminary pediatric data that it may be less robust [9].
- 3) There have been no treatment trials of amphetamines (AMP) in SCT and ADHD.

Examining the efficacy of AMP in SCT is important as the AMP stimulant class is more potent than the MPH class through a dual effect on adrenergic/dopaminergic pathways, which may be important for effects on SCT.

#### **1.5 Dose Rationale**

FDA data on adult short term dosing information from clinical trials show that doses of Vyvanse are 30 mg, 50mg or 70mg. The patients were initiated on these doses and then they were titrated up by 20mg with a maximum dose of 70mg.

CONFIDENTIAL

## 1.6 Research Risks & Benefits

### 1.6.1 Risk of Study Drug

Study drug risks with Vyvanse (Lisdexamfetamine Dimesylate) are decreased appetite, insomnia, upper abdominal pain, irritability, nausea and vomiting, weight decreased, dry mouth, dizziness, affect lability, rash, diarrhea, anxiety, anorexia, jittery feeling, and agitation. Patients will be told to take medication once daily in the morning and report if they have any of these effects at each visit [10].

Warnings and Precautions with Vyvanse (Lisdexamfetamine Dimesylate) are sudden death, stroke, and myocardial infarction (MI) reported in adults. Sudden death reported in children and adolescents with structural cardiac abnormalities and other serious heart problems [10]. Patients will have an electrocardiograph (EKG) prior to induction on Vyvanse (Lisdexamfetamine Dimesylate). Subjects will be monitored weekly for hypertension, tachycardia and any cardiac abnormalities. People with heart abnormalities will not be treated with amphetamines. These serious but uncommon side effects were reported by people who took Vyvanse. The following cardiovascular side effects (involving the heart and/or blood vessels) have been reported with the use of amphetamines:

- Sudden death
- Cardiomyopathy (enlargement of the heart or muscle weakness)
- Myocardial infarction (heart attack)
- Increased blood pressure
- Tachycardia (rapid heart rate)
- Palpitations (forceful, sometimes irregular heartbeats)

Vyvanse (Lisdexamfetamine Dimesylate) may exacerbate symptoms of behavior disturbance and thought disorder in patients with a preexisting psychotic disorder. Vyvanse may induce a mixed/manic episode in patients with bipolar disorder. Patients will be screened for any preexisting Axis 1 diagnosis, which would exclude them from the study.

CONFIDENTIAL

The following uncommon central nervous system side effects involving the brain and/or spinal cord have been reported with the use of amphetamine: stroke, psychotic episodes, mania, euphoria, depression, dysphoria, overstimulation, aggressive behavior, hostility, seizures, tremor, dyskinesia, exacerbation of phonic tics including Tourette's syndrome or motor tics, blurry vision, dizziness, restlessness, and headache. If during the course of the study patient develops any of these side effects including changes in mood, the study doctor will discontinue patient from the study and refer the patient to regular treatment.

Vyvanse (Lisdexamfetamine Dimesylate) is associated with decreased weight and growth in pediatric patients which will not be studied in this clinical trial. There are also these uncommon gastrointestinal side effects: diarrhea, constipation, urticaria, skin rashes, unpleasant taste, and other allergic reactions.

Vyvanse (Lisdexamfetamine Dimesylate) is also associated with peripheral vasculopathy, including Raynaud's phenomenon, which generally improves after dose reduction or discontinuation. Observe carefully for digital changes during treatment.

Sometimes people have allergic reactions to drugs. Allergic reactions can be mild or severe, but they should always be taken seriously. In rare cases, severe allergic reactions can be life-threatening.

Some things that happen during an allergic reaction are:

- A rash
- Having a hard time breathing
- Wheezing when you breathe
- Sudden drop in blood pressure
- Swelling around the mouth, throat, or eyes
- Fast pulse
- Sweating

**CONFIDENTIAL**

### **1.6.2 Other Risks of Study Participation**

There are other potential risks associated with participating in this study. Patients will be made aware of these risks. There is a minimal risk when obtaining blood samples, which include slight bruising, swelling, pain, blood clots, and a small risk of infection or a temporary feeling of faintness. Only experienced trained staff will perform phlebotomy on these patients. A minimal risk is associated with an EKG, which include an initial feeling of coldness when the test material touches your skin and a localized rash or skin irritation from the test material.

There is the risk associated with taking a placebo, which is similar to not taking medication for ADHD. When patients take placebo during the study, it is possible that their ADHD symptoms may return or get worse. The study doctor and the study staff will monitor these ADHD symptoms while the patient is taking the placebo.

There is a risk if patients stop their regular medication to be in the study; their ADHD symptoms may return or get worse. It would be vital to inform the patients to tell the study doctor or study staff right away if they have any problems.

The risk associated with stopping current ADHD medications before starting the study include: dizziness, nausea, headache, abnormal sensations in arms and legs, fatigue, vomiting, irritability, sleeplessness, diarrhea, anxiety, fainting, excessive sweating. These side-effects with similar drugs were temporary and usually resolved by themselves.

There is a possible risk of loss of confidentiality related to urine screens and clinical data obtained during this study. As a guard against the loss of confidentiality, all information will be stored in locked files which can be accessed only by members of the research staff for this project.

CONFIDENTIAL

### 1.6.3 Potential benefits

This research study includes procedures that may change the treatment patients with ADHD would otherwise receive. We hope knowledge gained will be of benefit to the patients. While there may not be a direct benefit to the patients, it is hoped that the knowledge gained will benefit others in the future.

## 2 Study Objectives

Primary Objective: The primary objective is to examine changes in ratings of ADHD symptoms and SCT. The primary measure of ADHD symptoms will be the total score on the ADHD Rating Scale (ADHD-RS) with prompts [16]. The primary measure of SCT will be the Barkley SCT Scale.

Secondary Objectives:

- 1) Examine changes in the BRIEF-A Metacognition Index and Motivation Subscales as these subscales are more closely related to measures of arousal and motivation than other subscales of the BRIEF-A.
- 2) Examine changes in ratings of functional impairment via the B Barkley Functional Impairment Scale (BFIS).
- 3) Examine changes in a battery of neuropsychological tests of arousal and alerting, including:
  - i. The Cambridge Neuropsychological Testing Automated Battery (CANTAB) ADHD battery: A validated battery of 4 tests which assess motor speed (Motor Control Task), spatial working memory (Spatial Working Memory), response inhibition (Stop Signal Task), and sustained attention (Rapid Visual Information Processing) [17]. In addition, we have included the Attention Switching Task (AST), an useful test in defining the cognitive phenotype in individuals with ADHD + high IQ. Measures of reaction time and reaction time variability will be

CONFIDENTIAL

examined.

- ii. The Wechsler Adult Intelligence Scale-IV (WAIS-IV): Coding and Symbol Search subtests will be used to evaluate processing speed [18].
- 4) Examine potential differences in nature and severity of ADHD symptoms (total, inattentive, and hyperactive-impulsive), symptoms of executive function (BRIEF GEC, metacognition, behavioral regulation scales and subscales: Inhibit, Shift, Emotional Control, Initiate, Working Memory, Plan/Organize, Organization of Materials, Monitor), neuropsychological test performance on the CANTAB and WAIS subtests listed above, and impairment ( Barkley Functional Impairment Scale (BFIS)) [27]
- 5) The On-Top scale will be used on treatment outcome in adult ADHD to measure executive functions in daily life.[29][30]

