### 3 Study Design

#### 3.1 General Design

- 1) Total number of subjects/Total sample size: Approximately 120 patients with ADHD (with the final number of subjects depending on the proportion of ADHD subjects who have SCT; we have based our projections on an estimated 50% prevalence) in the phenotype phase (screening visit); 50 adults with ADHD and SCT+ will enter the treatment phase with LDX and placebo. We will analyze data from all subjects who take at least one dose of medication in both blocks. Using a 20% drop-out rate to occur throughout the trial, we estimate that approximately 50 subjects will enroll in the trial; 46 patients will complete the first phase of treatment, 44 patients will complete the intervening placebo washout, and 40 patients will complete each treatment phase.
- 2) Justification for sample size: We will enroll a sufficient number of subjects to recruit 80 patients with ADHD and SCT to enter the treatment study. The 50% prevalence of SCT in adult ADHD has been established in community samples [1, 2]. Power for this study was calculated using PASS [22] based on the primary outcome, i.e. change between baseline and week 4 of treatment on the Barkley SCT scale. Previous studies suggest that the upper bound of the effect size for the comparison of ADHD

CONFIDENTIAL

medications vs. placebo for ADHD symptoms varies between 1.2 and 1.5 standard deviations. Using a conservative estimate of effect that is half as robust for SCT as ADHD we based on our calculations on a 0.6 ES for SCT symptoms. The primary comparison will be a reduction in SCT symptoms on LDX vs. placebo. With 45 evaluable patients with SCT we will have 80% power to detect an effect size (ES) of 0.6 using a two-sided test with a type I error of 0.05.

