### **3.2 Primary Study Endpoints**

The primary study endpoint is to examine the efficacy of lisdexamfetamine dimesylate (LDX) versus placebo on symptoms of sluggish cognitive tempo (SCT) in adults with ADHD and SCT.

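### Section 2 names two primary measures, Sections 3.1 and 3.2 name only SCT, and no section says which result counts as success

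*Combined protocol and SAP*

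**What the plan says.** Section 2 (Study Objectives) puts two symptom domains in one primary objective: "The primary objective is to examine changes in ratings of ADHD symptoms and SCT". It then names an instrument for each. The first is given as "The primary measure of ADHD symptoms will be the total score on the ADHD Rating Scale (ADHD-RS) with prompts", and the second domain gets its own sentence: "The primary measure of SCT will be the Barkley SCT Scale".

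Section 3.1 (General Design) names one. The power calculation is "based on the primary outcome, i.e. change between baseline and week 4 of treatment on the Barkley SCT scale". It adds: "The primary comparison will be a reduction in SCT symptoms on LDX vs. placebo". The stated power is for that comparison: "With 45 evaluable patients with SCT we will have 80% power to detect an effect size (ES) of 0.6". The error rate that goes with it is two-sided 0.05, given once and not divided between measures.

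Section 3.2 (Primary Study Endpoints) covers efficacy of the drug "versus placebo on symptoms of sluggish cognitive tempo (SCT) in adults with ADHD and SCT". It does not mention ADHD symptoms, and it gives no scale or time point.

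The ADHD-RS treatment effect is ranked nowhere else. The secondary endpoints in Section 3.3 concern the comparison of patients with and without SCT, and the secondary objectives in Section 2 do not list change in ADHD-RS on treatment. Section 7.2 (Statistical Methods) fits models to outcome ratings in general. It names no primary outcome, testing order, alpha split, or rule on whether one or both scales must succeed. Its responder criterion mentions a 30% decrease on both scales without saying whether one or both must be met.

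**The concern.** A reader cannot tell from the plan whether the ADHD-RS is a second primary endpoint. Two things are at stake.

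The first is error control. Two tests at 0.05, with success on either one enough, give a false-positive rate above 0.05 when the drug affects neither scale.

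The second is the meaning of a split result. The trial's question is SCT. The plan expects a smaller effect on SCT than on ADHD symptoms, and the Background section notes that response in patients with SCT may be weaker. An ADHD-RS success with an SCT failure is therefore foreseeable, and the plan gives two different answers on whether it is a success.

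**Working it through.** **Inputs from the plan (Section 3.1).** SCT effect 0.6 SD; ADHD-symptom effect 1.2 to 1.5 SD, described as an upper bound; 45 evaluable patients; two-sided 0.05; 40 patients expected to complete both treatment phases. The plan gives no correlation between the scales and none between periods within a patient, so the values used below are assumptions.

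**Step 1: reproduce the 80%.** Two-sample comparison with n = 45 per group and d = 0.6: noncentrality d × √(n/2) = 0.6 × √22.5 = 2.846.
- Noncentral t with 88 degrees of freedom: power 0.804.
- Normal approximation: power 0.812.
- n = 45 is the smallest n per group that reaches 80% by the t calculation.

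The stated figure therefore reproduces for SCT alone at an undivided 0.05.

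**Step 2: false-positive rate if either scale counts and neither responds.** For independent tests, 1 − 0.95² = 0.0975. For correlated test statistics, P(|Z1| > 1.96 or |Z2| > 1.96) from the bivariate normal:

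| Assumed correlation | Rate | Multiple of 0.05 |
|---|---|---|
| 0 | 0.0975 | 1.95 |
| 0.3 | 0.0951 | 1.90 |
| 0.5 | 0.0907 | 1.81 |
| 0.7 | 0.0835 | 1.67 |
| 0.9 | 0.0704 | 1.41 |

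If SCT is the sole primary, the rate is 0.05. If both scales are required, it is at most 0.05.

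**Step 3: chance of a positive ADHD-RS with a negative SCT result.** The Step 1 formula is applied to both scales.
- With 45: SCT fails with probability 1 − 0.804 = 0.196. ADHD-RS power at 1.2 SD is 0.9999. The split probability lies between 0.196 − 0.0001 and 0.196 whatever the correlation between scales, so about 20%.
- With 40: noncentrality 0.6 × √20 = 2.683. SCT power is 0.755 (t) or 0.765 (normal), so SCT fails with probability 0.245 or 0.235. ADHD-RS power at 1.2 SD is still above 0.999. The split probability is about 24%.
- Because 1.2 SD is part of an upper-bound range, take an assumed 0.8 SD instead. ADHD-RS power with 45 is 0.964, and the split probability is at least 0.196 − 0.036 = 0.16.

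**Step 4: sensitivity to the crossover.** The Step 1 formula ignores pairing. If 0.6 is scaled to the between-patient SD, a paired t test with 45 patients uses 0.6/√(2(1 − r)), where r is the within-patient correlation between periods.

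| Assumed r | SCT power, n = 45 | SCT fails, n = 45 | SCT fails, n = 40 |
|---|---|---|---|
| 0 | 0.795 | 0.205 | 0.256 |
| 0.3 | 0.914 | 0.086 | 0.122 |
| 0.5 | 0.976 | 0.024 | 0.041 |

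The 20% and 24% are therefore on the plan's own basis and fall if r is positive. In the other direction, if the drug has no effect on SCT and 1.2 SD on the ADHD-RS, SCT is non-significant 95% of the time and the split result is close to 95%.

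**The case against.** The strongest reply is that the plan does identify its primary. Section 3.1 says so twice, Section 3.2 is the section headed for it, and the power and alpha belong to SCT. Section 2 states objectives, and its phrase about the primary measure of ADHD symptoms can be read as choosing an instrument for that domain. This has weight: it shows which repair fits the plan. It does not remove the conflict, because Section 2 places ADHD symptoms inside the primary objective and no other section gives the ADHD-RS treatment effect a lower rank.

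A reader might infer that the false-positive rate is nearly doubled as the plan stands. The documents do not support that. It needs a rule that either scale suffices, which is never stated, together with low correlation and no true effect on either scale. Both scales are rated in the same patients at the same visits, so positive correlation is likely. A null ADHD-RS effect is also hard to credit: the protocol notes that the drug is approved for adult ADHD and plans on a large effect. If the ADHD-RS truly responds, the only possible false positive is on SCT, and that stays at 5%. The split result is then a problem of interpretation and not of error inflation.

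A reader might also infer that Section 7.2 tests every outcome at .05. It does not. The p < .05 there is a rule for dropping model effects; the only type I error for an efficacy test is the one Section 3.1 attaches to SCT.

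**Conclusion.** The point holds, and the text is wrong as written. Section 2 contradicts Sections 3.1 and 3.2 on the number of primary measures, and nothing in the plan settles whether one scale or both must succeed. That rests on the wording alone and is firm.

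The sizes are conditional. The false-positive rate could reach 9.8% only if either scale counts and neither responds, and it falls to 9.1% or 8.3% at assumed correlations of 0.5 or 0.7. The more practical exposure is the split result, at about 20% with 45 evaluable patients and about 24% with 40. Those figures assume the plan's effects of 0.6 SD and 1.2 SD and its unpaired formula. Positive within-patient correlation would lower them, and an SCT effect below 0.6 would raise them.

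**What to change.** Make the LDX–placebo difference in Barkley SCT Scale change, from baseline to week 4 of treatment in each period, the single primary endpoint at two-sided 0.05. Name the visits: Visit 6 for the first period and Visit 11 for the second. The visits matter because Week 4 in the schedule of procedures is Visit 6 only, and the second period ends at Week 10. Make the ADHD-RS total the key secondary endpoint, tested at two-sided 0.05 only if SCT is significant. This fixed sequence holds the error rate over the two tests at 0.05.

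Four sections need matching text, settled before unblinding:
- Section 2: SCT alone in the primary objective, with ADHD-RS change moved to the secondary objectives.
- Section 3.2: the scale and time point.
- Section 3.3: ADHD-RS change on treatment.
- Section 7.2: the primary outcome, the model contrast that tests it, and the testing order.

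The cost is wording, plus the loss of a confirmatory ADHD-RS claim if SCT fails. SCT alpha, power and sample size are unchanged. Requiring both scales to succeed would also resolve the conflict. Splitting alpha at 0.025 each would cut SCT power with 45 to 0.71 (t) or 0.73 (normal) and would need 53 (normal) to 55 (t) evaluable patients for 80%, by the same formula.
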